**12-January-2018**

## **Study design and participants**

This study is a randomised, two-arm, parallel dietary intervention trial. A 48-week dietary intervention programme was conducted in children aged 5-14 years with a diagnosis of NAFLD. The study participants were randomized into a low free sugar diet group and a regular diet group. As this was a dietary intervention study, the participants could not be double-blinded for the grouping and intervention. The primary objective of this study is to determine whether a low free sugar dietary intervention improves liver function, fasting glucose, fasting insulin, lipid profile and hepatic steatosis in children with NAFLD. The effects of the intervention will be analysed and compared at weeks 12, 24 and 48.

Overweight and obese children and their guardians who attended Shengjing Hospital of China Medical University between October 2018 and April 2020 were selected as study subjects. All guardians signed an informed consent form before participating in the intervention. Out of 150 subjects initially included, 146 were eligible for analysis after excluding those missing key variables.

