## **Intervention**

After baseline data collection, the intervention group received a 30-60 minute educational session with a dietitian and clinicians, including a health education prescription. Interventions occurred at weeks 1, 12 and 24, with routine evaluations of disease, diet, physical activity, and adherence. Follow-ups at 48 weeks assessed NAFLD extent, dietary profile, and health knowledge for both subjects and guardians.

Blinding was not possible due to the researchers' roles in the intervention.

However, laboratory and imaging tests were conducted by separate hospital departments, with physicians unaware of group assignments, minimizing potential bias.

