### **Statistical analysis**

The questionnaire and laboratory examination data were entered into a database using EpiData 3.1 software, and the disputed data were determined by looking at the original data. The statistical descriptions of continuous variables were expressed as mean±standard deviation (Mean±SD), and after the normality test, t-test or analysis of variance (ANOVA) was used to compare the groups; the paired t-test was used to determine the differences between baseline and post-intervention hepatic fat scores, body composition, and serum analytical variables in the groups; the statistical descriptions of the categorical variables were expressed in the form of frequency (rate) and analyzed by the  $\chi^2$  (chi-squared) test; the post-intervention versus baseline indices were analyzed by the  $\chi^2$  (chi-squared) test. The test was used for analysis; the difference between the post-intervention and baseline indicators was used as an evaluation index of the intervention effect. The data were processed and analyzed using SPSS 23.0 software, and the two-sided P value of less than 0.05 was statistically different, with a test level of  $\alpha=0.05$ .

In the present study, the physical and laboratory indicators of children with NAFLD were measured longitudinally by repeated measures over a 48-week period, and generalized estimating equations (GEEs) were used to deal with the internal correlation, to test for the interactions between time and subgroups and the potential

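### The primary objective spans five unranked domains at three visits with no primary endpoint, decisive visit, success rule or multiplicity adjustment, so the 0.05 level does not protect the trial's main claim

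*Combined protocol and SAP*

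**What the plan says.** The section Study design and participants gives one primary objective: whether the low free sugar diet "improves liver function, fasting glucose, fasting insulin, lipid profile and hepatic steatosis in children with NAFLD". That is five domains, in no order of importance. The next sentence adds three time points: "The effects of the intervention will be analysed and compared at weeks 12, 24 and 48". The same section already reports the analysis population: "Out of 150 subjects initially included, 146 were eligible for analysis".

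The Statistical analysis section sets one threshold for everything: "the two-sided P value of less than 0.05 was statistically different". It describes two routes to a between-group result. One is the simple comparison: "after the normality test, t-test or analysis of variance (ANOVA) was used to compare the groups". The other is a GEE for the repeated measurements, used among other things "to test for the interactions between time and subgroups". Neither is called the primary analysis.

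The text contains no primary variable, decisive visit, ranking, composite, rule for when the objective is met, or multiplicity adjustment.

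**The concern.** A primary objective needs a stated result that would count as meeting it, and this plan gives none. A reader could require all five domains to improve, or accept any one of them, at any visit, by either analysis.

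The choice determines the error rate. Under an all-five rule the unadjusted 0.05 is safe. Under an any-one rule every extra domain and visit is another chance of a false positive, and the type I error for the objective rises well above 5%. The GEE does not help here: it accounts for correlation among one child's repeated values of one outcome, not for error across outcomes.

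The practical risk is that one P<0.05, such as one lipid result at week 12, is reported as success on the primary objective. Some or all data appear to have been collected already, so the rule could also be chosen after the results are known.

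**Working it through.** **Inputs from the documents**
- Domains: 5; visits: 3; arms: 2 (section Study design and participants).
- Level: 0.05 two-sided, that is 0.025 in the favourable direction, with no allocation across tests (section Statistical analysis).
- Analysed: 146.

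**Assumed, because the documents do not give them**
- Correlation between outcomes and between visits: 0 to 0.9.
- Equal arms of 73 (146/2), for the power figures only.
- One variable per domain. The analytes in the liver and lipid panels are not listed; more than one per panel would raise the error figures.

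**Number of primary tests**
- Every domain at every visit: 5 × 3 = 15.
- Steatosis compared at week 48 only, as "Follow-ups at 48 weeks assessed NAFLD extent" in the Intervention section might suggest: 4 × 3 + 1 = 13.
- One GEE test per domain: 5.

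**The plan's own figure.** For one test, 1 − 0.95¹ = 0.05. The stated level is correct per comparison.

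**Chance of at least one false positive, independent tests**
- Any direction, 1 − 0.95ᵏ: k = 5 gives 0.226; k = 13 gives 0.487; k = 15 gives 0.537.
- Favourable direction only, 1 − 0.975ᵏ: 0.119; 0.280; 0.316.

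**Correlated tests.** These figures come from 400,000 multivariate-normal draws under no effect anywhere, with exchangeable correlation between outcomes and between visits. Each cell gives any direction / favourable only.

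| Correlation (outcomes / visits) | 15 tests | 13 tests | 5 tests |
|---|---|---|---|
| 0 / 0 (exact) | 53.7% / 31.6% | 48.7% / 28.0% | 22.6% / 11.9% |
| 0.5 / 0.7 | 36.2% / 18.2% | 33.5% / 16.8% | 18.2% / 9.1% |
| 0.9 / 0.9 | 16.3% / 8.2% | 15.5% / 7.8% | 10.2% / 5.1% |

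**Ratio to the nominal level**
- Any direction: 10.2/5 = 2.0 to 53.7/5 = 10.7.
- Favourable only: 5.1/2.5 = 2.0 to 31.6/2.5 = 12.6.

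**All-five rule, no effect anywhere.** Chance of success is at most about 1.7%, reached at correlation 0.9.

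**Holm across five week-48 tests.** With no effect anywhere, Holm rejects something only if the smallest P is at or below 0.05/5 = 0.01. If independent, 1 − 0.99⁵ = 0.049. By simulation it is 0.042 at correlation 0.5 and 0.023 at 0.9. It never exceeds 0.05.

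**Power cost of Holm** (normal approximation, continuous outcome)
- Standard error in SD units: √(2/73) = 0.1655.
- Effect detectable with 80% power at 0.05: (1.960 + 0.842) × 0.1655 = 0.464 SD.
- At 0.01: (2.576 + 0.842) × 0.1655 = 0.566 SD.
- Power at 0.01 for a 0.464 SD effect: Φ(0.464/0.1655 − 2.576) = Φ(0.226) = 0.589.

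**The case against.** The strongest reply is that the objective joins the five domains with a conjunction, so read literally the diet must improve all of them. On that reading there is no inflation. This stands as far as it goes: the error rate is conditional on an any-one reading. But the plan does not adopt the all-five rule, and under either reading it does not say what result meets the objective. That gap does not depend on any assumed correlation.

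The 53.7% figure needs independence between visits of the same child, which the plan's own use of GEE contradicts. That is fair: it is an upper end, not an estimate for this trial. In the intermediate case (0.5/0.7) the fifteen-test figure is 36.2%.

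A significant worsening could not be presented as improvement, so the favourable-only figures suit the argument better. That is also fair, but they have to be set against 2.5%, and the ratio of 2 to about 13 is no smaller.

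The plan's GEE interaction test would naturally be a joint test over visits, with no direction. The favourable-only column for five tests therefore applies to a single contrast per domain. The any-direction figure barely moves: a three-degree-of-freedom version at 0.9/0.9 gives 10.6% against 10.2%.

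The plan also says the GEE is used to obtain valid intervention effect estimates, which favours the five-test count. The thirteen-test count is a tentative reading. Five tests still at least double the nominal error.

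**Conclusion.** The concern holds and should be fixed before any result is called confirmatory. The definite defect is that the primary objective has no success criterion: five domains, three visits and two unranked analyses share one unadjusted 0.05.

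If any one significant result may support the objective, the false-positive chance is 10.2–22.6% for five tests and 16.3–53.7% for fifteen. For false claims of benefit it is 5.1–11.9% and 8.2–31.6%, against 2.5%. These ranges rest on assumed correlations of 0 to 0.9 and one variable per domain. Every case in the range is at least about twice the nominal level.

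**What to change.** Name the GEE between-group difference at week 48, the end of the 48-week programme, as the primary comparison. Name one variable for each of the five domains, apply Holm across the five at two-sided 0.05, and claim success only for the domains that pass. Alternatively, name a single primary outcome at week 48 and test it at 0.05. In either case, label the week 12 and 24 comparisons, the remaining analytes and the within-group paired tests as secondary or exploratory.

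If outcome data have already been seen, say so and describe the choice as post hoc. In that case Holm across all five domains is preferable to picking one. The disclosure must also cover the choice of analyte within the liver and lipid panels, because Holm across domains does not correct for selection inside a panel.

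The cost is in wording and labelling; no new data are needed. Some nominally significant results can no longer be called confirmatory. At the strictest Holm step (0.01), an effect with 80% power at 0.05 has 59%, and the effect detectable with 80% power rises from 0.46 to 0.57 SD, assuming 73 per arm. Later Holm steps are less strict. The SD figures apply to continuous outcomes and would not carry over if steatosis is analysed as ordinal. A single primary outcome has no such power loss.

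### The primary analysis should cover all randomised children, not the 146 left after an undefined missing-data exclusion

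*Combined protocol and SAP*

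**What the plan says.** The Study design and participants section describes a randomised, two-arm, open-label dietary trial and sets three comparison times: "The effects of the intervention will be analysed and compared at weeks 12, 24 and 48". The same section fixes who is analysed. Of 150 children first included, "146 were eligible for analysis after excluding those missing key variables".

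The available text does not say:
- which variables count as key, or whether they are baseline or follow-up measures;
- whether the four were removed before or after randomisation;
- which arm they came from, the allocation ratio, or the arm sizes.

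The Statistical analysis section lists t-tests or ANOVA, paired t-tests, chi-squared tests and a GEE. The GEE is used because "the physical and laboratory indicators of children with NAFLD were measured longitudinally by repeated measures over a 48-week period". The only data-handling rule there concerns disputed entries, not missing ones. No all-randomised, intention-to-treat or full analysis set is named.

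On blinding, "the participants could not be double-blinded for the grouping and intervention", but the Intervention section adds that "laboratory and imaging tests were conducted by separate hospital departments, with physicians unaware of group assignments".

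**The concern.** In a randomised trial the protected comparison is between all children as allocated. A rule that removes children for incomplete data can undo that protection if it acts after allocation and if incompleteness is related to arm and outcome. Families here knew their diet, so attendance could differ between arms. Blinded laboratory and imaging staff protect the measurements, but not against who stops attending.

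The rule also sits badly with the planned model. A GEE can use a child who has some visits and not others. Removing the child altogether discards whatever visits were observed. The plan has several outcome domains (liver function, glucose, insulin, lipids, steatosis), so a child missing one variable may have had usable data on the rest.

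**Working it through.** **Step 1: what the exclusion could mean.** The sentence fits three situations, with different consequences.

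| When removed | What was missing | Consequence |
|---|---|---|
| Before randomisation | Anything | The child was never in the randomised set. No departure and no bias. |
| After randomisation | A baseline value | Departs from analysis as randomised and loses any follow-up visits, but selection is not driven by arm or outcome. |
| After randomisation | A follow-up value | Departs from analysis as randomised, can bias the comparison, and loses any other visits the child had. |

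Bias therefore needs two unknowns to hold together: removal after randomisation, and missing follow-up data.

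**Step 2: inputs.** From the plan: 150 included, 146 analysed, two-sided alpha 0.05. The plan gives no sample-size, SD or dropout figure, so there is no design calculation to reproduce. Assumed: the 150 are the randomised children, allocation is 1:1 (75 per arm), and excluded children differ from the rest of their arm by d = 0.5 to 1 SD.

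**Step 3: precision.**
- Excluded: 150 - 146 = 4, and 4/150 = 2.7%.
- Interval width: sqrt(150/146) = 1.014, so about 1.4% wider.
- Power, if it were 80% with 150 children: Phi(2.802 x sqrt(146/150) - 1.96) = 78.9%.
- Difference detectable at 80% power, (1.960 + 0.842) x sqrt(4/N): 0.457 SD with 150 and 0.464 SD with 146.

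**Step 4: shift in the arm difference.** Dropping a fraction f of an arm whose members differ from the rest by d moves that arm's mean by f x d. With d the same size and direction in both arms, shift = (difference in number excluded / 75) x d. If loss is unrelated to arm, the chance of each split is hypergeometric, with C(150,4) = 20,260,275.

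| Split | Chance | Shift for d = 0.5 to 1 SD |
|---|---|---|
| 2:2 | C(75,2)^2 / C(150,4) = 0.38 | 0 |
| 3:1 | 2 x C(75,3) x 75 / C(150,4) = 0.50 | (2/75) x d = 0.013 to 0.027 SD |
| 4:0 | 2 x C(75,4) / C(150,4) = 0.12 | (4/75) x d = 0.027 to 0.053 SD |

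If the differences ran in opposite directions in the two arms, the effects would add instead of cancelling. The total still could not exceed (4/75) x 1 = 0.053 SD at d = 1.

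**Step 5: scale.** For a 4:0 split, the standard error of the arm difference is sqrt(1/71 + 1/75) = 0.166 SD. The shift is then 0.027/0.166 = 0.16 to 0.053/0.166 = 0.32 standard errors.

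**Step 6: sensitivity to the allocation ratio.** With 2:1 allocation and all four from the arm of 50, the shift is (4/50) x d = 0.04 to 0.08 SD. The standard error is sqrt(1/46 + 1/100) = 0.178 SD, so this is 0.22 to 0.45 standard errors.

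**Step 7: the 146.** The plan gives no count of missed visits among the 146. The number may be zero, and no size can be put on it from the documents.

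**The case against.** The strongest reply is that the four may never have been randomised. The plan says only that 150 were included at the start. Even if they were randomised, a missing baseline value would explain the exclusion as well as a missing visit. A reader might infer that these are post-randomisation dropouts removed because of their outcomes. The text does not support that. This objection stands in full, and it makes both the conclusion and the fix conditional.

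A reader might also infer that attrition at weeks 12, 24 and 48 undermines the results, or that the analyses rest on different children. On the second, "the paired t-test was used to determine the differences between baseline and post-intervention hepatic fat scores" and "the difference between the post-intervention and baseline indicators was used as an evaluation index of the intervention effect" both need complete pairs, whereas the GEE does not. Either inference requires missed visits among the 146, and none is reported. If the key variables are follow-up outcomes, the 146 may be largely complete on them.

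The document is dated January 2018, yet it describes children attending "between October 2018 and April 2020 were selected as study subjects". A reader might infer that the rule was chosen after the data were seen. The text does not distinguish a planned rule from a reported result, so that cannot be concluded.

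Finally, the text available for review stops partway through the GEE derivation, so a missing-data statement could have followed. That weakens any argument from silence. It does not remove the exclusion sentence, which is explicit and restricts the analysis.

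**Conclusion.** The concern holds as a point about the primary analysis set. The plan limits the analysis to 146 of 150 children by an undefined missing-data rule, and the available text offers no all-randomised alternative. If any of the four had been randomised, that departs from analysis as randomised and discards any visits the GEE could have used. Bias follows only if exclusion depended on missing follow-up data.

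The likely size is small: 2.7% of children, intervals about 1.4% wider, and a shift of 0 to about 0.05 SD, at most about 0.3 standard errors. The shift rests on 75 per arm and a 0.5 to 1 SD difference, neither of which is in the documents. The case for change is that the better analysis is standard, cheap and already within reach of the planned model. It does not rest on any demonstration that the result is distorted.

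**What to change.** Make the primary set all randomised children in their assigned arm, using every available visit in the planned GEE. Keep the 146-child analysis as a sensitivity analysis.

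Report the four by arm, by timing relative to randomisation and by missing variable. If none was randomised, say so; the set then stays as it is. Report the number of children with data at weeks 12, 24 and 48 in each arm.

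If those counts show missing outcomes, add a simple missing-data sensitivity analysis. Unweighted GEE generally needs data missing completely at random, and a child with no follow-up outcome adds little to it, so enlarging the set does not by itself deal with such children. Imputation with values shifted by arm is one option but is not required. Across several outcome domains and three visits it would be substantially more work, and the size of the shift would need justifying.

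The cost is revised wording and a little more analysis work. No new data are needed.

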## **Intervention**

After baseline data collection, the intervention group received a 30-60 minute educational session with a dietitian and clinicians, including a health education prescription. Interventions occurred at weeks 1, 12 and 24, with routine evaluations of disease, diet, physical activity, and adherence. Follow-ups at 48 weeks assessed NAFLD extent, dietary profile, and health knowledge for both subjects and guardians.

Blinding was not possible due to the researchers' roles in the intervention.

However, laboratory and imaging tests were conducted by separate hospital departments, with physicians unaware of group assignments, minimizing potential bias.

### **Statistical analysis**

The questionnaire and laboratory examination data were entered into a database using EpiData 3.1 software, and the disputed data were determined by looking at the original data. The statistical descriptions of continuous variables were expressed as mean±standard deviation (Mean±SD), and after the normality test, t-test or analysis of variance (ANOVA) was used to compare the groups; the paired t-test was used to determine the differences between baseline and post-intervention hepatic fat scores, body composition, and serum analytical variables in the groups; the statistical descriptions of the categorical variables were expressed in the form of frequency (rate) and analyzed by the  $\chi^2$  (chi-squared) test; the post-intervention versus baseline indices were analyzed by the  $\chi^2$  (chi-squared) test. The test was used for analysis; the difference between the post-intervention and baseline indicators was used as an evaluation index of the intervention effect. The data were processed and analyzed using SPSS 23.0 software, and the two-sided P value of less than 0.05 was statistically different, with a test level of  $\alpha=0.05$ .

In the present study, the physical and laboratory indicators of children with NAFLD were measured longitudinally by repeated measures over a 48-week period, and generalized estimating equations (GEEs) were used to deal with the internal correlation, to test for the interactions between time and subgroups and the potential

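### For body measures in children aged 5-14 followed for 48 weeks, the plan specifies neither an age- and sex-standardised scale nor adjustment for age and sex

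*Combined protocol and SAP*

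**What the plan says.** All references are to the combined protocol and SAP.

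- **Population and duration** (Study design and participants): "A 48-week dietary intervention programme was conducted in children aged 5-14 years with a diagnosis of NAFLD". There is a concurrent control: "The study participants were randomized into a low free sugar diet group and a regular diet group".
- **Within-arm test** (Statistical analysis): a paired t-test is applied to "differences between baseline and post-intervention hepatic fat scores, body composition, and serum analytical variables in the groups".
- **Effect index** (same section): "the difference between the post-intervention and baseline indicators was used as an evaluation index of the intervention effect".
- **Between-arm test** (same section): t-test or ANOVA after a normality check, with no covariates.
- **Longitudinal model** (same section): a GEE is fitted to physical and laboratory indicators with interactions involving time. Covariates appear only as a generic vector, and none is listed.
- **Primary objective** (Study design and participants): whether the diet "improves liver function, fasting glucose, fasting insulin, lipid profile and hepatic steatosis in children with NAFLD". No body measure is among these.

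The documents do not name the body measures or give their scale. They mention no z-score, centile, growth reference or height indexing, and no age or sex term.

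**The concern.** Over 48 weeks a growing child's weight, BMI, fat mass and lean mass are expected to change without any intervention, by an amount that depends on age and sex. On such a scale, zero change does not mean no effect, and a rise is not necessarily a worsening. A plan that makes change the index of effect, and also tests it within each arm, therefore lets expected growth feed directly into a P value.

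The comparison between arms raises a different issue. A 5-year-old and a 13-year-old have different expected gains. Unless age and sex are accounted for, that spread sits in the residual variance. Adjusting for the baseline value alone does not fully remove it, because two children with the same baseline fat mass can differ in age, sex and expected growth.

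At stake are the interpretation of any within-arm statement about body measures and the precision of the between-arm estimates for them. Leaving the scale open also allows it to be chosen after the results are known.

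**Working it through.** The plan has no sample-size calculation, SD or effect size, so there is no design figure to reproduce. What follows is illustrative.

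**Inputs from the documents.** Two-sided alpha of 0.05. For the numbers: "Out of 150 subjects initially included, 146 were eligible for analysis after excluding those missing key variables".

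**Assumptions.** 1:1 allocation (the ratio is not stated), so 146/2 = 73 per arm. Body measures on a raw scale. Expected 48-week weight gain spread evenly from 2 to 6 kg across the age range. Individual SD of weight change around that expectation of 2, 3 or 4 kg.

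**Step 1: within-arm test, no diet effect.** Let d be mean growth divided by the SD of change. Then P(reject) = 1 − Φ(1.96 − d√73) + Φ(−1.96 − d√73), with √73 = 8.544.

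| d | P(reject) |
|---|---|
| 0 | 5% |
| 0.1 | 14% |
| 0.25 | 57% |
| 0.5 | 99% |
| 1.0 | about 100% |

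A simulation of 20,000 t-tests gave 56% at d = 0.25 and 99% at d = 0.5. Under the weight assumptions the mean gain is (2 + 6)/2 = 4 kg. The SD of change is √(SD² + 1.33), with 1.33 from Step 3. So d runs from 4/√17.33 = 0.96 to 4/√5.33 = 1.73, where rejection is close to certain.

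**Step 2: between-arm contrast.** With mean growth g in both arms and diet effect δ, the expected difference in change is (g + δ) − g = δ. In the same simulation with δ = 0, the two-sample test rejected 5.0% of the time at d = 0.25 and 5.1% at d = 0.5, with a mean difference of about 0. Common growth therefore does not bias the comparison.

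**Step 3: noise left in the contrast.** An even spread over 2 to 6 kg has variance (6 − 2)²/12 = 1.33, an SD of 1.15 kg. Growth share = 1.33/(SD² + 1.33). SE ratio = √((SD² + 1.33)/SD²). Equivalent number of children = 146 × (1 − share).

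| Individual SD | Growth share of variance | SE ratio | Equivalent number |
|---|---|---|---|
| 4 kg | 1.33/17.33 = 7.7% | 1.04 | 135 |
| 3 kg | 1.33/10.33 = 12.9% | 1.07 | 127 |
| 2 kg | 1.33/5.33 = 25% | 1.15 | about 110 |

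**Step 4: power.** With 73 per arm the difference detectable with 80% power is (1.96 + 0.84) × √(2/73) = 0.464 SD of raw change. Removing 10%, 20% or 30% of the variance multiplies this by √(1 − share), giving 0.440, 0.415 or 0.388 SD. Power for a 0.464 SD effect rises from 80% to 84%, 88% or 92%.

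Steps 3 and 4 assume that the adjustment removes all the age-related growth variance, so they show the most that could be gained under these inputs.

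**The case against.** The strongest reply has four parts.

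1. **The scale is not stated.** A reader might infer that raw weight, BMI or fat mass is analysed. The documents do not show this, because none of these variables is named, and body composition could mean percent fat. This stands: the supportable finding is that no standardisation or adjustment is specified. It does not remove the gap, since percent fat also varies with age and sex.
2. **There is a randomised control.** A reader might infer that growth biases the estimated diet effect. It does not: Step 2 shows that it cancels in expectation, and the same applies to a group-by-time term in the GEE. The mixing of growth with effect is confined to change read within one arm. The direction also depends on the measure. For fat mass or BMI, growth would tend to hide a benefit rather than create one.
3. **The GEE allows covariates.** Age and sex adjustment is not excluded. That is correct, but it is not stated either, and the t-test or ANOVA on change has none.
4. **The consequences are modest.** No body measure is in the primary objective, and a standard error 4% to 15% larger is a moderate cost resting on assumed inputs. This stands and limits the weight of the point.

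It is also true that a raw-scale comparison between arms, adjusted for age and sex, is valid. Raw values need not be barred from inference.

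**Conclusion.** The concern holds in a limited form. For body measures in children aged 5-14 over 48 weeks, the plan specifies neither an age- and sex-standardised scale nor age and sex adjustment, while naming post-minus-baseline change as the index of effect and testing it within arms. If the measures are on a raw scale, within-arm change cannot separate growth from diet: a drift of only 0.25 SD of change makes a paired test in 73 children significant 57% of the time with no diet effect. The randomised contrast remains unbiased. Its cost is precision, with a standard error about 4% to 15% larger. That range rests on the assumed gain of 2 to 6 kg and individual SD of 2 to 4 kg, not on any figure in the documents. The documents do not support reading this as a threat to the primary objective; it bears on secondary conclusions about body measures.

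**What to change.** In the Statistical analysis section:

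- Name each body measure and its scale.
- For these measures, base effect claims on the between-arm contrast: the GEE group-by-time term or a model of change.
- Include baseline value, baseline age and sex as covariates. In the GEE, add their interactions with time, because main effects alone do not absorb growth rates that differ by age and sex. In a model of change, main effects of age and sex do that work.
- Analyse BMI as an age- and sex-specific z-score, or as percent of the reference 95th centile, where a reference exists.
- State that within-arm change in raw body measures is not read as an intervention effect.

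The cost is a few sentences, a few extra model terms and a recode. The recode needs age, sex, height and weight; the documents do not list these as recorded, but selecting overweight and obese children by age makes it very likely that they were. One drawback is that BMI z-scores compress at severe obesity, which is why percent of the 95th centile is offered as an alternative.
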